- The patient presents with, or has a history of, an Axis I (DSM-5TM) diagnosis of Bipolar Disorder, PTSD, OCD, Autism, Pervasive Developmental Disorder (PDD), or Schizophrenia or Schizoaffective Disorder.
- The patient has a diagnosis of attention-deficit/hyperactivity disorder (ADHD) and is not maintained on a stable dose of a methylphenidate or amphetamine for a minimum of 4 weeks prior to the study treatment.
- One of the parents or siblings of the patient has a history of Bipolar Disorder.
- The patient has attempted suicide or is at significant risk of suicide (either in the opinion of the investigator or defined as a "yes" to suicidal ideation questions 4 or 5 or answering "yes" to suicidal behaviour on the C-SSRS within the last 12 months).
- The patient has a known intellectual disability (as suggested by an intelligence quotient [IQ] < 70), or, clinical evidence or known social or school history indicative of intellectual disability.).
- The patient has been treated with any antidepressant or anxiolytic medication within 2 weeks prior to Visit 2 (only *de novo* patients).
- The patient is unable to swallow capsules.
- The patient has previously been treated with vortioxetine in a clinical study (only *de novo* patients).

Investigational Medicinal Product, Reference Therapy, Doses and Mode of Administration

Open-label Period

- Vortioxetine – 5, 10, 15, and 20 mg/day, tablets, orally
The treatment should be taken once daily, preferably at the same time each day.
- Patients will receive a targeted dose of 10 mg/day vortioxetine, however the investigator has the possibility to adjust the dose in case of unsatisfactory response or in case of dose-limiting AEs. The patient will receive a lower initial dose (5 mg/day for 2 days) prior to receiving 10 mg/day. The dose can be up- or down-titrated with 5 mg/day. The patient should receive the same dose for 2 days before being up- or down-titrated to a new dose.

Double-blind Period

- Vortioxetine – 5, 10, 15, and 20 mg/day, encapsulated tablets, orally
- Placebo – encapsulated tablets, orally

The treatment should be taken once daily, preferably at the same time each day.

Statistical Methodology

- The following analysis sets will be used to analyse and present the data:
 - *all-patients-enrolled set* (APES) – all patients enrolled to the 12-week open-label, flexible-dose treatment period who took at least one dose of IMP

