5.3 Selection Criteria

Patients will be recruited *de novo* (enrolled to the open-label period) as well among those who complete treatment in lead-in Study 12709A (enrolled to the open-label period) or remitters from Study 12712A (randomized to the double-blind period).

Patient selection is based on the inclusion and exclusion criteria listed below.

Patients who meet each of the inclusion criteria at the Screening Visit and Baseline (unless otherwise specified) and none of the exclusion criteria at the Screening Visit and Baseline (unless otherwise specified) are eligible to participate in this study.

For patients rolling over from Studies 12709A or 12712A, their data from Studies 12709A and 12712A - including Inclusion Criteria - will be used for this study (see also section [11.1.2](#)).

Inclusion Criteria for *de novo* patients

1. The patient is capable of communicating with the site personnel.
2. The patient and/or the patient's parent(s)/legal representative(s) are able to read and understand the *Informed Assent/Consent Form*.

3. The patient and the patient's parent(s)/legal representative(s) have signed the *Informed Assent/Consent Form*.
4. The patient and the patient's parent(s)/legal representative(s) are willing and able to attend study appointments within the specified time windows.
5. The patient is an outpatient consulting a clinician.
6. The patient has a primary diagnosis of MDD according to DSM-5™ although co-morbid anxiety disorders will be permitted (except Post Traumatic Stress Disorder (PTSD) and Obsessive Compulsive Disorder (OCD)). The diagnoses will be confirmed using the K-SADS-PL.
7. The patient has a CDRS-R total score ≥ 45 at the Screening and Baseline Visits.
8. The patient has a CGI-S ≥ 4 at the Screening and Baseline Visits.
9. The patient is boy or girl aged ≥ 7 and < 12 years at screening. Patients who turn 12 years during this study will be allowed to continue in the study.
10. Contraception criterion, if applicable: The patient, if a girl who is sexually active and of childbearing potential (defined as girls aged ≥ 10 years and younger girls who, at the discretion of the investigator, are deemed to be of reproductive potential), must use adequate contraception from the Screening Visit until 30 days after the last dose of IMP.

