2. In the investigator's opinion, the patient could benefit from participation in a study which includes continued treatment with vortioxetine.
3. The patient is in remission at the last 2 visits in Study 12712A, in which the CDRS-R is assessed every 4 weeks. Hence
 - a. If the patient rolls over at Visit 7 or Visit 8 (Week 8 or Week 10): the patient has a CDRS-R total score ≤ 28 at Visit 5 (Week 4) and Visit 7 (Week 8) in Study 12712A
 - b. If the patient rolls over at Visit 9 (Week 12): the patient has a CDRS-R total score ≤ 28 at Visit 7 (Week 8) and Visit 9 (Week 12) in Study 12712A
4. The patient has been on a stable dose of vortioxetine for the past 4 weeks prior to rollover to this study.
5. The patient is a child aged ≥ 7 and <12 years at Baseline of Study 12712A.

Exclusion Criteria (*de novo* patients, rollover patients from Studies 12709A and 12712A)

1. The patient has previously been enrolled in this study.
2. The patient is a member of the study personnel or of their immediate families, or is a subordinate (or immediate family member of a subordinate) to any of the study personnel.
3. The patient is pregnant or breastfeeding.
4. The patient has a history of severe drug allergy or hypersensitivity, or known hypersensitivity or intolerance to any of the IMP(s) or its/their excipients.
5. The patient has previously been treated with vortioxetine in a clinical study (applicable only to *de novo* patients). Patients who previously participated in 12709 study and were withdrawn prior to randomization may participate.
6. The patient is under forced treatment.
7. The patient receives ongoing current psychotherapy that is planned to be intensified. Interpersonal psychotherapy (IPT) or cognitive behavioural therapy (CBT) are not allowed.
8. The patient has hereditary problems of fructose intolerance, glucose-galactose malabsorption, or sucrose-isomaltase insufficiency.
9. The patient has any current psychiatric disorder (DSM-5TM criteria) different from MDD, established as the primary diagnosis, as assessed using The Kiddie-Schedule for Affective

Disorders and Schizophrenia for School-aged Children, Present and Lifetime version (K-SADS-PL).

10. The patient suffers from intellectual disability, organic mental disorders, or mental disorders due to a general medical condition (DSM-5™ criteria).

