11. The patient has a known intellectual disability (as suggested by a known intelligence quotient [IQ] <70), or, clinical evidence or known social or school history indicative of intellectual disability.
12. The patient has any other disorder for which the treatment takes priority over treatment of MDD or is likely to interfere with study treatment or impair treatment compliance.
13. The patient has a history of moderate or severe head trauma or other neurological disorders or systemic medical diseases that are, in the investigator's opinion, likely to affect central nervous system functioning.
14. The patient has a diagnosis of ADHD that requires a pharmacological treatment that cannot be maintained on a stable dose of an appropriate stimulant medication for a minimum of 4 weeks prior to the Baseline Visit.
15. The patient has a known first degree relative with a history of Bipolar Disorder.
16. The patient is unable to swallow capsules.
17. The patient has a history of cancer, other than basal cell or Stage 1 squamous cell carcinoma of the skin, that has not been in remission for >5 years prior to the first dose of IMP.
18. The patient has or has had one or more of the following conditions that is/are considered clinically relevant in the context of the study.
 - neurological disorder
 - other psychiatric disorder
 - cardiovascular disease
 - seizure disorder or encephalopathy
 - congestive heart failure
 - cardiac hypertrophy
 - arrhythmia
 - bradycardia (heart rate <50 beats per minute [bpm])
 - respiratory disease
 - hepatic impairment or renal insufficiency
 - metabolic disorder
 - endocrinological disorder
 - gastrointestinal disorder
 - haematological disorder
 - infectious disorder
 - any clinically significant immunological condition
 - dermatological disorder
 - venereal disease

- elevated intra-ocular pressure or is at risk of acute narrow-angle glaucoma

19. The patient takes or has taken recent or concomitant medication that is disallowed or allowed with restrictions (specified in [Appendix II](#)) or it is anticipated that the patient will require treatment with at least one of these medications during the study.

20. The patient has one or more clinically significant out-of-range vital signs at the Screening Visit (*de novo* patients, or at the last visit of Studies 12709A or 12712A for rollover patients).

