8.3 Baseline Visit Open-label Period (Visit 2)

De novo patients who continue to meet all inclusion criteria and none of the exclusion criteria (see section 5.3) will be enrolled into a 12-week open-label treatment period.

For patients rolling over from Study 12709A, the Baseline Visit will be performed the same day as the Week 12 (Completion) Visit of Study 12709A. The ICF must be signed before any Study 13546A-related activities take place. The eligibility criteria should be confirmed based on the evaluation of the latest data available in Study 12709A.

For 12709A patients, values from assessments and procedures (efficacy/safety, including blood/urine samples and use of concomitant medication) performed at the Completion Visit (Visit 12) in Study 12709A will be the Baseline Visit values in Study 13546A (detailed in Panel 2 and section 11.1.2). Please note that the hormones laboratory tests are specific for the 13546A study and will have to be collected using a separate kit at the same time as collecting the blood samples required by the 12709A protocol. Assessments that are not part of the Completion visit in 12709A (that is, examinations, Tanner staging, and menstrual cycle) will

be performed as part of the 13546A Baseline Visit. Patients eligible for entering the open-label period will start IMP (vortioxetine) at the Baseline Visit. Patients will start with 5 mg/day as detailed in section 6.1.

The schedule of assessments during the open-label period is described in [Panel 2](#).

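### The synopsis bars any child with a current or past diagnosis from a named psychiatric list; Section 5.3 covers that list only in part and largely by discretion, and its ADHD rule differs

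*Protocol*

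**What the plan says.** **Synopsis, Main Exclusion Criteria.** A child is excluded when "The patient presents with, or has a history of, an Axis I (DSM-5TM) diagnosis of Bipolar Disorder, PTSD, OCD, Autism, Pervasive Developmental Disorder (PDD", with schizophrenia and schizoaffective disorder completing the list. The rule covers past as well as current diagnoses, whether or not they are primary. It leaves no room for judgement and, unlike two other synopsis exclusions, is not limited to de novo patients. On ADHD, the synopsis excludes a child who has the diagnosis "and is not maintained on a stable dose of a methylphenidate or amphetamine for a minimum of 4 weeks prior to the study treatment".

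**Protocol Section 5.3.** This section presents its own lists as the operative ones: "Patient selection is based on the inclusion and exclusion criteria listed below". Section 8.3 points back to it for de novo children, "who continue to meet all inclusion criteria and none of the exclusion criteria (see section 5.3) will be enrolled", and Section 8.4 does the same for children rolling over from Study 12712A. The criteria closest to the synopsis rule are:
- De novo inclusion 6 requires primary MDD, "although co-morbid anxiety disorders will be permitted (except Post Traumatic Stress Disorder (PTSD) and Obsessive Compulsive Disorder (OCD".
- Exclusion 9: "The patient has any current psychiatric disorder (DSM-5TM criteria) different from MDD, established as the primary diagnosis".
- Exclusion 18 reaches present and past conditions and has a generic entry for other psychiatric disorders, but applies only to those judged clinically relevant to the study.
- Exclusion 15: "The patient has a known first degree relative with a history of Bipolar Disorder".
- Exclusion 14, on ADHD: "The patient has a diagnosis of ADHD that requires a pharmacological treatment that cannot be maintained on a stable dose". The dose in question is of a suitable stimulant, over at least 4 weeks before Baseline.

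**The concern.** A synopsis should summarise the body of the protocol and should not be stricter than it. Here the synopsis gives a fixed answer for a set of diagnoses, while the list that sites are told to use leaves most of those cases to judgement. A site that follows Section 5.3 exactly could give a child whom the synopsis bars up to 12 weeks of open-label treatment and then 26 weeks in the double-blind period.

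The text also leaves it unclear whether such an enrolment is a protocol deviation, although Section 14 says that no permission to deviate will be given. Section 16.2 defines no per-protocol set, so once randomized and dosed these children stay in the full-analysis set and in the primary analysis.

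Bipolar disorder shows the gap most plainly. The protocol screens for manic symptoms with the GBI and excludes on family history, yet the Section 5.3 exclusions name bipolar disorder only in relatives.

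**Working it through.** The check compares the two lists. No arithmetic is needed to establish the point.

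**Step 1: which synopsis exclusions have a counterpart in Section 5.3?** The synopsis has eight main exclusions. Seven have a numbered counterpart among the 27 exclusions: ADHD (14), bipolar disorder in the family (15), suicide risk (27), intellectual disability (11), recent antidepressant or anxiolytic use (26), inability to swallow capsules (16) and previous vortioxetine (5). The named psychiatric diagnoses are the only item without one.

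**Step 2: run typical cases through both lists.** "Discretion" is not a category in the protocol; in the table, *by judgement* means excluded only if exclusion 18, or a general ground such as exclusion 12, 24 or 25, is invoked.

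| Child | Synopsis | Section 5.3 |
|---|---|---|
| De novo, current co-morbid PTSD or OCD | Excluded | Excluded (inclusion 6) |
| De novo, past PTSD or OCD | Excluded | By judgement; inclusion 6 does not mention history |
| Any source, a listed disorder that is current and primary | Excluded | Excluded (exclusion 9) |
| Any source, current non-primary bipolar disorder, autism/PDD or schizophrenia-spectrum disorder | Excluded | By judgement |
| Any source, past bipolar or schizophrenia-spectrum disorder | Excluded | By judgement |
| Rollover, non-primary or past PTSD or OCD | Excluded | By judgement; inclusion 6 is for de novo patients only |
| ADHD, stable methylphenidate or amphetamine for at least 4 weeks | Not excluded | Not excluded |
| ADHD needing drug treatment, no stable stimulant dose | Excluded | Excluded (exclusion 14, on its natural reading) |
| ADHD, unmedicated and not needing drug treatment | Excluded | Not excluded by exclusion 14 |

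The lists agree in the first, third, seventh and eighth rows. In the last row they give opposite answers. In the other four, a fixed exclusion stands against a discretionary one.

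**Step 3: does the mismatch touch the stated power?** Inputs from Section 16.10: 40 patients per group, relapse rates of 0.42 and 0.69, one-sided 5%.
- Hazard ratio = ln(1 − 0.69) / ln(1 − 0.42) = 2.150, matching the stated 2.15.
- Expected relapses = 40 × 0.42 + 40 × 0.69 = 16.8 + 27.6 = 44.4.
- Schoenfeld power = Φ(√(44.4/4) × ln 2.150 − 1.645) = 81.7%, consistent with the stated minimum of 80%.

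Eligibility does not enter any of these formulas, so the power statement stands as it is.

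**The case against.** The strongest reply is that Section 5.3 has more cover than a quick comparison suggests. Inclusion 6 settles co-morbid PTSD and OCD in de novo children. Exclusion 9 settles any other current primary disorder. Exclusion 18 does reach psychiatric history. Exclusion 19 with Appendix II bars children taking or expected to need antipsychotics or mood stabilisers. Section 8.2.1 requires a form for every de novo patient to be reviewed by the contract research organisation, with confirmation before enrolment. Since Sections 8.3 and 8.4 send every site to the same list, two sites need not be working from different rules.

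All of this stands, and it narrows the point. A reader might infer that Section 5.3 has no relevant criterion at all, or that every child with unmedicated ADHD is eligible under it. The documents support neither: the cover is partial, and the clear ADHD conflict is confined to ADHD that does not require drugs.

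The reply does not close the gap. Exclusion 18 turns on a judgement that the synopsis does not allow. Exclusion 19 turns on medication, not diagnosis. Section 8.2.1 does not say which list is applied in the central review. Even if all sites use Section 5.3, its answer can differ from the synopsis.

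**Conclusion.** The inconsistency holds in this form: a categorical rule in the synopsis against partial and largely discretionary cover in Section 5.3, plus a separate ADHD conflict. It concerns non-primary or past bipolar and schizophrenia-spectrum diagnoses, non-primary autism/PDD, past PTSD or OCD, non-primary PTSD or OCD in rollover patients, and unmedicated ADHD not requiring drugs. It bears on which children are treated, and it is cheap to remove.

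Its size in patients cannot be computed, because the documents give no prevalence for these diagnoses. A reader might infer that a few such children would distort a result resting on about 44 relapses, or that these conditions would raise the CDRS-R score or trigger relapses unrelated to MDD. The documents give no calculation or source for either. Allocation is randomized 1:1, and no bias between arms has been shown.

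Two assumptions remain. Parent-study criteria may already screen rollover patients, but they are not in the documents. Inclusion 6 also requires a DSM-5 diagnosis of MDD; the DSM-5 text is not available here, so whether it closes part of the gap on its own cannot be judged. The documents do not show which of the two lists was intended.

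**What to change.** Reconcile the synopsis Main Exclusion Criteria with Section 5.3 so that both carry the same psychiatric-history criterion and the same ADHD criterion, word for word, with the sponsor stating which rule it intends. The text should settle four things:
- whether a past or non-primary diagnosis excludes;
- whether any discretion applies;
- whether the criterion covers rollover patients;
- whether a child with unmedicated ADHD not requiring drugs is eligible.

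Section 8.2.1 should name the list used in the pre-enrolment review.

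No new assessment is needed for de novo children under either choice. The K-SADS-PL, which covers current and past episodes (Section 9.1.3), is already done at screening, alongside psychiatric and neurological history (Section 9.1.1). For children from Study 12709A, Panel 2 carries these data over. Panel 3 schedules no K-SADS-PL for those from Study 12712A, so the amendment should say which transferred data are used.

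The cost is a wording amendment and, depending on the rule chosen, possibly the loss of a few de novo candidates.

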 - *all-patients-randomized set* (APRS) – all patients randomized to the 26-week double-blind treatment period
 - *full-analysis set* (FAS) – all patients randomized to the 26-week double-blind treatment period who took at least one dose of double-blind IMP
- The efficacy analyses will be based on the FAS.
- Primary analysis:
 - Primary efficacy analysis will compare the time to relapse (defined as either a total score ≥ 40 on the CDRS-R with a history of 2 weeks of clinical deterioration, or clinical deterioration as judged by the clinician) between Vortioxetine and placebo using a Cox regression model with exact adjustment for ties. A one-sided 5% level of significance will be used. Patients not relapsing before Week 26 will be censored at Week 26 and patients withdrawing due to other reasons than relapse will be censored at time of withdrawal.
- Sensitivity analysis of the primary endpoint:
 - Primary analysis will be repeated ignoring relapses occurring during the first week, two weeks and four weeks of the double-blind period, respectively.
 - The number of relapses will be summarized according to relapse criteria: CDRS-R total score ≥ 40 with 2 weeks of clinical deterioration, investigator's judgement, or both.
 - Primary analysis will be repeated for the *de novo* patients and for the (pooled) 12709A patients and 12712A patients.
- Analyses of secondary endpoints:
 - Relapse over 26 weeks will be analysed using logistic regression.
 - Secondary efficacy variables (CDRS-R, PQ-LES-Q, CGI-S, CGI-I) will, on an exploratory basis be analysed over the 26-week double-blind period by Mixed Model Repeated Measurements (MMRM) and analysis of covariance (ANCOVA) (observed cases [OC] and last observation carried forward [LOCF]).
 - The population pharmacokinetics (popPK) of vortioxetine in children will be analysed through non-linear mixed effect analysis and will be described in a separate popPK analysis plan.
- Analyses of other endpoints:
 - On an exploratory basis, potential use of psychotherapy in the double-blind period, severity of illness, gender, and age will be assessed as covariates or to generate subgroups for the Cox regression model.
 - Descriptive statistics will be used to compare patient populations and treatment outcome between the geographical regions.
- The safety analyses will be based on the APES and the FAS.
- Analyses of safety endpoints:

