16.8.6 Analysis of the Exploratory Endpoint(s)

No formal exploratory endpoints have been defined.

On an exploratory basis, severity of illness, gender and age will be assessed as covariates or to generate subgroups for the Cox regression model as described in section [16.8.2](#).

In addition, descriptive statistics will be used to compare patient populations and treatment outcome between the geographical regions.

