7.2 Withdrawals

The number of patients who withdrew from the Open Label Period will be summarized by *de novo* patients, rollover patients from Study 12709A and total. The number of patients who withdrew from the Double-Blind Treatment Period will be summarized by treatment group and total. The primary reason for withdrawal as well as all reasons for withdrawal will be presented per period.

Patients who withdrew from the study will be listed and the listing will include the number of days in the study until withdrawal from the study, the number of days on IMP, the primary reason for withdrawal, and all reasons for withdrawal.

8 Demographics and Baseline Characteristics

Summary tables on demographic and baseline characteristics will be presented for both the Open Label Period and the Double-Blind Treatment Period separately. The baseline characteristics for the Open Label Period will be based on the APES and will be presented for *de novo* patients, rollover patients (from Study 12709A) and overall.

For the Double-Blind Treatment Period the summary tables on demographics will be based on the FAS and results will be presented per treatment group (vortioxetine and placebo) and in total.

Demographics (sex, age, ethnicity and race), baseline characteristics (height, weight and BMI), disease characteristics and baseline efficacy variables will be summarized.

The following baseline (randomization) efficacy variables will be summarized:

CDRS-R total score

CGI-S score

PQ-LES-Q scores (total score and overall score (item 15))

Disease characteristics will include MDE history (MDD history, including number of MDEs, duration of current episode, treatment type (psychotherapy / pharmacotherapy) for MDD. In addition, MDD treatment will be summarized.

Medical history from the Medical History eCRF page will be coded with medical dictionary for regulatory activities (MedDRA) version 19.0 or above. All medical histories, data on major depressive disorder history and treatment, the family psychiatric history and the history of stimulant medication will be listed.

9 Recent and Concomitant Medication

Recent and concomitant medication will be coded using the WHO Drug Dictionary (WHO Global B3 Mar 2020).

Medications will be classified according to the start and stop time and summarized by anatomical therapeutic chemical (ATC) code, generic drug name:

- medication discontinued prior to first dose of IMP in Open Label Period

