11.3.2 Sensitivity Analyses of the Primary Endpoint

The following sensitivity analyses will be performed:

1. The primary analysis will be repeated ignoring relapses occurring during the first week, two weeks and four weeks of the Double-Blind Treatment Period, respectively.

For the purpose of this sensitivity analysis 3 subsets of data will be defined:

- i) A subset excluding all patients with a relapse within the first 7 days after the start of the Double-Blind Treatment Period.
- ii) A subset excluding all patients with a relapse within the first 14 days after the start of the Double-Blind Treatment Period.
- iii) A subset excluding all patients with a relapse within the first 28 days after the start of the Double-Blind Treatment Period.

The primary analysis of the study, as described, will be repeated in each of the 3 subsets above and for each subset the hazard ratio for vortioxetine compared to placebo will be estimated from the model and presented with p-values and 95% CIs.

2. The primary analysis will be repeated for the *de novo* patients and for the (pooled) 12709A patients and 12712A patients additionally.

The hazard ratio's for vortioxetine compared to placebo will be estimated from the model and presented with p-values and 95% CIs for *de novo* and rollover patients (pooled 12709A and 12712A) separately.

On an exploratory basis, if feasible, the impact of the use of psychotherapy, severity of illness, gender and age may be investigated. Therefore, these may be added as fixed factors or covariates to the Cox regression model, or subgroups may be created.

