11.5 Analysis of the Exploratory Endpoints

No formal exploratory endpoints have been defined.

On an exploratory basis, severity of illness, gender and age may be assessed as covariates or to generate subgroups for the Cox regression model as described in section 11.3.1.1. In addition, descriptive statistics will be used to compare patient populations and treatment outcome between the geographical regions.

Also on an exploratory basis, the primary analysis of the study will be repeated for each of the two definitions of relapse below and the hazard ratio for vortioxetine compared to placebo will be estimated from the model and presented with p-values and 95% CIs:

- i) Relapse based on investigator judgement.
- ii) Relapse defined as CDRS-R total score ≥ 40 with 2 weeks of clinical deterioration

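### Exploratory Cox analyses may condition on psychotherapy used after randomization, which could create a false subgroup difference; limit the factor to status at or before randomization

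*Protocol*

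**What the plan says.** Four places list factors for exploratory use with the Cox model, and they differ.

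- **Protocol Synopsis, Statistical Methodology (analyses of other endpoints):** on an exploratory footing, "potential use of psychotherapy in the double-blind period, severity of illness, gender, and age will be assessed as covariates" or used to form subgroups.
- **Protocol 16.8.6:** the same list without psychotherapy: "On an exploratory basis, severity of illness, gender and age will be assessed as covariates or to generate subgroups".
- **SAP 11.3.2:** psychotherapy is kept but made optional, and the reference to the double-blind period is gone: "On an exploratory basis, if feasible, the impact of the use of psychotherapy, severity of illness, gender and age may be investigated". On method, "these may be added as fixed factors or covariates to the Cox regression model, or subgroups may be created".
- **SAP 11.5:** psychotherapy is again absent: "On an exploratory basis, severity of illness, gender and age may be assessed as covariates or to generate subgroups".

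No section restricts the variable to status at randomization, treats it as time-dependent, or comments on interpretation. The primary model (Protocol 16.8.2, SAP 11.3.1) contains treatment and the CDRS-R total score at randomization, stratified by inclusion source. It has no psychotherapy term.

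On data, SAP section 8 lists "treatment type (psychotherapy / pharmacotherapy) for MDD" among disease characteristics, and Protocol 9.1.1 records MDD treatment type and outcome at screening for de novo patients. Panel 3 has no psychotherapy item at the Randomization Visit.

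**The concern.** Gender, age and severity at entry are fixed before treatment is assigned, so randomization balances them between arms on average within any level. Psychotherapy use in the double-blind period is not fixed in that way. If some children start it because they are getting worse, and more children worsen on placebo, then use depends both on treatment and on the approaching relapse. Users are then a group selected partly on the outcome, and selected differently in the two arms. Comparing arms within users or within non-users, or adjusting for use, no longer compares like with like.

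At stake is an exploratory statement about whether the effect of vortioxetine differs with psychotherapy. Such statements are reported and read, and in a trial of 80 children an artefact of definition would be hard to recognize afterwards.

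**Working it through.** **1. Plan's own figures (Protocol 16.10, SAP section 14).** Relapse over 26 weeks is 0.69 on placebo and 0.42 on vortioxetine, with 40 per arm and a one-sided 5% test.

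- Hazard ratio = ln(1 − 0.69)/ln(1 − 0.42) = 2.15 as stated, or 1/2.15 = 0.465 for vortioxetine against placebo.
- Expected relapses = 40 × 0.69 + 40 × 0.42 = 44.4.
- Power (Schoenfeld) = Φ(√(44.4/4) × ln 2.15 − 1.645) = Φ(0.906) = 0.817, which agrees with at least 80%.

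The documents give no figure for the psychotherapy analysis, so its size has to be shown over assumed ranges.

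**2. Hand calculation.** Give every child the same true hazard ratio, 0.465. Assume psychotherapy is used by a share *a* of relapsers and 10% of others. With relapse probability p in an arm:

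- relapse among users = a·p / (a·p + 0.1(1 − p))
- relapse among non-users = (1 − a)·p / ((1 − a)·p + 0.9(1 − p))

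For a = 0.30:

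- Users: placebo 0.207/0.238 = 0.870; vortioxetine 0.126/0.184 = 0.685. Ratio of cumulative hazards = ln(0.315)/ln(0.130) = 0.57.
- Non-users: placebo 0.483/0.762 = 0.634; vortioxetine 0.294/0.816 = 0.360. Ratio = ln(0.640)/ln(0.366) = 0.44.

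The same steps for the other values of *a*, beside Cox fits to simulated data (20,000 to 40,000 patients per scenario, several runs):

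| Use in relapsers / others | Users, by hand | Users, Cox | Non-users, by hand | Non-users, Cox | Adjusted HR, Cox |
|---|---|---|---|---|---|
| 10% / 10% | 0.465 | 0.46 | 0.465 | 0.46–0.49 | – |
| 20% / 10% | 0.53 | 0.55 | 0.46 | 0.45 | 0.47 |
| 30% / 10% | 0.57 | 0.56–0.60 | 0.44 | 0.44–0.45 | 0.48–0.485 |
| 40% / 10% | 0.59 | 0.61 | 0.43 | 0.43 | 0.50 |

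The spread between runs is simulation error. The first row is the control: without dependence there is no gap in truth.

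**3. A different mechanism.** Children move from well to worsening to relapse, calibrated to 0.42 and 0.69. Assumed: 15% already in psychotherapy at randomization, a probability q of starting at worsening, and a mean of 2 or 4 weeks from worsening to relapse. Users are all who ever use it.

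| q | Users | Non-users |
|---|---|---|
| 0 | 0.47 | 0.46–0.47 |
| 0.1 | 0.51–0.52 | 0.46 |
| 0.3 | 0.58–0.59 | 0.43 |
| 0.5 | 0.61–0.64 | 0.39–0.40 |

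With the factor defined at randomization, the values are 0.46–0.48 in users and 0.46–0.47 in non-users at every q.

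**4. At n = 80 (4-week lag).** A two-sided 5% interaction test rejects in 4.4% (q = 0), 7.8% (q = 0.3) and 11.7% (q = 0.5) of trials. One-sided power of the treatment test adjusted for ever-use is 0.81, 0.76 and 0.69, against 0.80–0.81 unadjusted. With no treatment effect, subgroup hazard ratios stay near 1 and the interaction test rejects in about 5–6%.

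**The case against.** The case for leaving the text alone has four parts.

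- **Status.** The analysis is exploratory in the protocol, optional in the SAP, and absent from two of the four lists. This stands and keeps the point minor. A reader might infer that the primary hazard ratio or its test is compromised. The documents do not support that, because psychotherapy is in neither the primary model nor the secondary ones.
- **Mechanism.** No section says that worsening leads to psychotherapy. Deterioration that in the investigator's view calls for changed treatment already counts as relapse, and relapsers leave the study, so some starts would fall after the endpoint. Exclusion criterion 7 bars IPT, CBT and ongoing psychotherapy that is planned to be intensified, so many users may simply be continuing. This narrows the path but does not close it: the withdrawal criteria do not name starting psychotherapy, and Appendix II covers medication only.
- **Direction.** A reader might infer that the analysis would show vortioxetine working less well alongside psychotherapy. That is too strong. Longer relapse-free follow-up also gives more time to become a user. When starts were simulated at a constant rate unrelated to worsening (10–30% over 26 weeks), hazard ratios were 0.39–0.49 in users and 0.47–0.49 in non-users, with no consistent shift.
- **Practical effect.** At 30%/10% use, about 40 × 0.238 + 40 × 0.184 ≈ 17 of 80 children would be users, and a false interaction would seldom reach significance. That is fair, but exploratory subgroup results are usually read from point estimates.

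**Conclusion.** The concern holds as a minor, conditional one. The synopsis names a post-randomization variable as a Cox covariate or subgroup factor, and the SAP does not repair this. If worsening prompts some psychotherapy starts, the exploratory result could show a subgroup difference where none exists. With use of 20–40% in relapsers against 10% in others, the hazard ratio would be roughly 0.53–0.61 in users and 0.46–0.43 in non-users, with an adjusted value of 0.47–0.50, against a true 0.465 throughout. Only the range is meaningful, because the usage rates, the lag and the prevalence at randomization are all assumed.

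The distortion needs a real treatment effect, or some other effect of treatment on psychotherapy use. In the simulations it did not raise false positives when the drug did nothing.

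**What to change.** - In the Protocol Synopsis and SAP 11.3.2, limit any psychotherapy covariate or subgroup to status known at or before randomization (yes/no).
- Summarize psychotherapy started or changed during the double-blind period by arm, descriptively only.
- Align Protocol 16.8.6 and SAP 11.5 with the chosen text. While doing so, state that severity of illness means severity at randomization: CDRS-R and CGI-S are rated at every double-blind visit, and no time point is given.

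**Cost.** The wording is cheap; the data need checking. MDD treatment-type history is recorded, but for 12709A rollovers it comes from that study's screening data, and no item for psychotherapy ongoing at randomization is shown in Panel 3. The sponsor should confirm that it is captured, especially for 12712A rollovers. If it is not, use the recorded history or keep psychotherapy descriptive only. The primary analysis, sample size and power do not change.
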